5.5 Treating the patient

Sponsor qualified medical personnel will be readily available to advise on trial related medical questions or problems.

5.5.1 Patient numbering

Investigators will screen patients only when a cohort is active for enrollment. Each patient is uniquely identified by a Subject Number which is composed by the site number assigned by Novartis and a sequential number assigned by the investigator. Once assigned to a patient, the Subject Number will not be reused.

Upon signing the informed consent form, the patient is assigned the next sequential number by the investigator. The investigator or his/her staff will contact the IRT and provide the requested identifying information for the patient to register them into the IRT. The site must select the case report/record form (CRF) book with a matching Subject Number from the Electronic Data Capture (EDC) system to enter data. In case that a patient signs the informed consent form during the pause of study, the IRT will inform the investigator that the patient cannot be enrolled.

If the patient fails to be treated for any reason, the IRT must be notified within 2 days that the patient was not treated. The reason for not being treated will be entered on the Screening period Study Disposition CRF.

5.5.2 Dispensing the study drug

Each study site will be supplied with study drugs in individual packaging for each patient.

The study drug packaging has a 2-part label for KAE609. A unique medication number is printed on each part of this label which corresponds to one of the treatment arms and dose. Coartem will not have 2-part label, the medication number will be printed on the main panel. Investigator staff will identify the study drug package(s) to dispense to the patient by contacting the IRT and obtaining the medication number(s). Immediately before dispensing the package to the patient, investigator staff will detach the outer part of the label from the packaging and affix it to the source document (Drug Label Form) for that patient's unique subject number.

If a patient vomits study drugs, KAE609 within 30 min or Coartem within 1 hour of intake, a replacement dose will be given to the patient and the investigator or designee will notify IRT (see [Section 5.5.4](#)).

Medication number and quantity of treatment drug taken by patients have to be collected by the investigator or designee.

5.5.3 Handling of study and additional treatment

5.5.3.1 Handling of study treatment

Study treatment must be received by a designated person at the study site, handled and stored safely and properly, and kept in a secured location to which only the investigator and designees

have access. Upon receipt, all study treatment must be stored according to the instructions specified on the labels. Clinical supplies are to be dispensed only in accordance with the protocol.

Medication labels will be in the local language and comply with the legal requirements of each country. They will include storage conditions for the study treatment but no information about the patient except for the medication pack number.

The investigator must maintain an accurate record of the dispensing of study treatment in a drug accountability log. The study treatment will be administered to patients under hospital supervision. Monitoring of drug accountability will be performed by monitors during site visits or remotely and at the completion of the trial.

At the conclusion of the study, and as appropriate during the course of the study, the investigator will return all unused study treatment, packaging, drug labels, and a copy of the completed drug accountability log to the Novartis monitor or to the Novartis address provided in the investigator folder at each site.

5.5.3.2 Handling of additional treatment

The following non-study treatment will be provided by the Sponsor and has to be monitored specifically:

- Coartem as rescue medication

Details are described in the CRF completion guidelines.

5.5.4 Instructions for prescribing and taking study treatment

KAE609

KAE609 can be administered irrespective of the timing of food intake.

Study medication will be administered by the study center personnel with approximately 180-240 ml of water. Each subject's mouth must be checked to ensure that the medication was swallowed. In the case that the patient vomits within 30 minutes of intake a replacement dose will be given to the patient and the investigator or designee will notify IRT. If the second dose is vomited the patient has to be given Coartem as rescue medication.

Coartem

Patients will be dosed BID for 3 days (at the following time points: 0, 8, 24, 36, 48, and 60 hours) and must receive a standard meal within 30 min prior to dosing, as per label. In the case that the patient vomits within 1 hour of intake a replacement dose will be given to the patient and the investigator or designee will notify IRT. If the second dose is vomited the patient has to be given non-lumefantrine standard of care.

Conventional 80/480 mg tablets or 20/120 mg tablets are to be taken orally with a glass of water. The dispersible tablet is to be dissolved in 10 mL of water in a small cup, and subsequently administered orally under hospital supervision; thereafter the cup will be rinsed with an additional 10 mL of water and the content is to be swallowed again.

Coartem medication should be followed whenever possible by food/drink (broth, sweetened condensed milk, etc.) as appropriate.

All dosages prescribed and dispensed to the subject during the study must be recorded on the Dosage Administration Record (DAR) CRF.

All kits of study treatment assigned by the IRT will be recorded in the IRT.

5.5.5 Permitted dose adjustments and interruptions of study treatment

Additional doses can be given in case of vomiting (see [Section 5.5.4](#)). These changes must be recorded on the Dosage Administration Record (DAR) CRF.

Otherwise, investigational or other treatment dose adjustments and/or interruptions are not permitted.

5.5.6 Rescue medication

The following circumstances warrant discontinuation of study treatment and the implementation of rescue medication (see [Section 6.5.8](#)):

Early treatment failure (ETF)

ETF is defined within this protocol as:

1. Clinical decline or lack of improvement (per Investigator) at 24 hours after first dose of treatment.
2. Development of any clinical complications (described in the WHO definition of complicated/severe malaria (WHO Guidelines 2010)) in the presence of parasitaemia within 72 hours of the first dose of treatment
3. Parasitaemia $> 75\ 000/\mu\text{L}$ at or after 12 hours post-dose
4. Parasitaemia \geq baseline with or without fever at 36 hours after first dose of treatment
5. Any parasitaemia based on microscopy with fever, 48 hours post-dose
6. Parasitaemia $> 100/\mu\text{L}$ based on microscopy with or without fever, 72 hours post-dose

Late Clinical Failure (LCF)

Development of danger signs or severe malaria on any day between Study Day 5 and Day 29 in the presence of parasitaemia without previously meeting any of the criteria of ETF.

Presence of parasitaemia and axillary temperature $\geq 37.5^\circ\text{C}$ on any day between Study Day 5 and Day 29 without previously meeting any of the criteria of ETF.

Late Parasitological Failure (LPF)

Presence of parasitaemia on any day between Study Day 5 and Day 29 and axillary temperature $< 37.5^\circ\text{C}$ without previously meeting any of the criteria of ETF or LCF.

Commencement of rescue medication with Coartem may occur after start of trial medications and up to Study Day 28 as deemed necessary by the investigator. Any patient on KAE609 who

did not need rescue medication up to Study Day 28, will be given Coartem at end of the study at Study Day 29. Rescue medication according to local guidance will be used for severe malaria.

Patients randomized to Coartem and meeting treatment failure definition will be further treated by rescue medication as per local treatment guidance.

The patients receiving rescue medication will not be replaced and will not discontinue the study (i.e., all the examinations as per the assessment schedule and all CRF pages for this patient will need to be completed).

Safety blood tests (Full Blood Count (FBC) and blood chemistry) will be collected on the initial day of rescue medication dosing. Blood films and blood sampling for parasite count and genotyping must be taken before giving the rescue treatment.

Patients treated with at least one dose of trial medications will continue to be followed-up until Study Day 29 according to schedule.

Use of rescue medication (including exact rescue regimen and route of administration) must be recorded on the electronic case report form (eCRF).

5.5.7 Prior and concomitant medication

Prior medications are defined as drugs taken and stopped prior to first dose of study medication.

Concomitant medication is defined as any medication, other than the Investigational Medicinal Product (IMP), which is given at least once between the day of first dose of randomized study medication and the last day of study visit (including those which were started pre-baseline and continued into the treatment period), including prescription and over-the-counter medicines, and any traditional or herbal remedies.

Paracetamol as an antipyretic, and metopimazine for repeated vomiting (or if not available, any other antiemetic which is not known to prolong QT and/or cause torsade de pointes) will be allowed. If paracetamol or equivalent drug is given as an antipyretic up to 72 hours prior first dose, it has to be reported as prior medication

Metoclopramide is contraindicated from the period prior to first dose to Day 5 post-dose (120 hours).

Beta-lactam antibiotics can be given in case of a bacterial infection appearing after enrolment. All other antibiotics, new-quinolones included, should be avoided where possible.

The investigator must instruct the patient to notify the study site about any new medications he/she takes after the patient was enrolled into the study. All medications, procedures and significant non-drug therapies (including herbal therapy, physical therapy and blood transfusions) administered after the patient was enrolled into the study must be recorded in the concomitant medications eCRF.

Each concomitant drug must be individually assessed against all exclusion criteria/prohibited medication. If in doubt the investigator should contact the Novartis medical monitor before randomizing a patient or allowing a new medication to be started.

5.5.8 Prohibited medication

Use of the following treatments is NOT allowed as per below recommendation in **KAE609 Cohorts**:

- Antimalarials other than the study drug and rescue medication (Coartem) are not permitted during the entire study period.
- Herbal medication should not have been taken within 1 week before the study treatment is given and should be avoided until the last study visit.
- Any other investigational treatment for the whole study duration.
- KAE609 undergoes CYP3A4 metabolism thus potent and moderate CYP3A inhibitors (such as HIV antivirals: e.g., ritonavir miscellaneous: e.g., clarithromycin, itraconazole, ketoconazole, grapefruit juice, verapamil, cimetidine) and inducers (such as HIV antivirals: e.g., efavirenz miscellaneous: e.g., barbiturates, carbamazepine, phenytoin, rifampin, St. John's wort) are not allowed up to 14 days before enrolment in the study or minimum 5 half-lives of the perpetrator drug (whichever is longer) administration and up to 7 days post administration.
- KAE609 is a potent inhibitor of CYP2C19 and can potentially increase the exposure of drugs which are a substrate of CYP2C19 by many folds (such as Proton pump inhibitors: e.g., lansoprazole, omeprazole, anti-epileptics: e.g., phenytoin, miscellaneous: e.g., amitriptyline, chloramphenicol, clomipramine, indomethacin, nelfinavir, progesterone (synthetic progestins used in hormonal contraceptives are not prohibited since they are metabolized by CYP3A4), proguanil, propranolol, warfarin). Therefore, these are prohibited for the treatment duration and 7 days after last dose.
- Drug known to cause QTc prolongation or known to be potentially hepatotoxic (see [Appendix 4](#)) are prohibited for the treatment duration and 7 days after last dose.

Apart from the above mentioned possible interactions in vitro data suggest KAE609 is inhibitor of CYP2B6, CYP2C9, CYP2A6, CYP1A2, CYP2D6, CYP2C8, and CYP3A4, however, assessment including SimCYP simulation suggests that potential change in the exposure of drug substrate of any of these would be less than two fold and unlikely to be of clinical significance. Nonetheless caution should be exercised such as staggering the dose of victim drug by ~12 hours from last dose of KAE609.

Use of the following treatments is NOT allowed as per below recommendation in **Coartem/Riamet Cohorts**:

Coartem/Riamet prescribing information should be followed in general. Use of any prescription drugs (with particular attention to use of CYP3A4 inhibitors, e.g., erythromycin, ketoconazole, itraconazole, cimetidine or CYP3A4 inducers e.g., rifampin, phenobarbital etc. Also drugs metabolized by CYP2D6 like flecainide, metoprolol, imipramine, amitriptyline, clomipramine, neuroleptics and those that increase QTc interval like terfenadine, astemizole, cisapride) is prohibited during study and within four (4) weeks prior to dosing. Herbal supplements are also prohibited during study and within one week prior to dosing. Medication which may be required to treat adverse events can be administered considering the potential interaction. Administration of paracetamol (daily total dose not to exceed 3g) / acetaminophen is acceptable, but dose and time of administration must be documented in the Concomitant medications / significant non-drug therapies section of the eCRF.

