3.1 Study design

This will be a multicenter, open label, randomized, dose escalation study to evaluate the hepatic safety and tolerability of KAE609 in adult patients (≥ 18 years and ≥ 45 kg bodyweight) with uncomplicated malaria caused by *P. falciparum*.

Starting dose of KAE609 will be a single dose of 10 mg and following acceptable safety results in the 10 mg treatment arm, the dose of KAE609 will be increased stepwise up to a single dose of 225 mg and multiple doses of 50 mg (QD x3 days) according to schedule below (Figure 3-1).

Based on the safety pattern observed in previous studies with KAE609, LFT parameters, if they rise, are expected to peak within 14 days of treatment. Hence, the decision to escalate to next cohort with higher doses will be based on the criteria as specified in the table below (Table 3-1):

Table 3-1 Decision criteria for dose escalation based on LFT results with KAE609

LFT parameter	Baseline	Maximum post baseline value	Decision to escalate to next cohort
ALT/AST	Within ULN	< 2 times ULN (from Day 1 to Day 15)	Escalate to next cohort after notification to safety review committee, after all the patients in the cohort have been followed for at least 14 days post treatment (study Day 15).
	> 1 to ≤ 1.5 ULN	< 2 times baseline (from Day 1 to Day 15)	
ALT/AST	Within ULN	≥ 2 to < 3 times ULN (from Day 1 to Day 15)	Escalate to next cohort based on review of liver safety (and any other relevant data) by safety review committee, after all the patients in the cohort have been followed for at least 28 days post treatment (Study Day 29)
	> 1 to ≤ 1.5 ULN	≥ 2 to < 3 times baseline (from Day 1 to Day 15)	
ALT/AST	Any baseline value	≥ 2 Grade (CTCAE grades) increase from baseline (at any time point during the study) in: 
 - 2 patients in a 10 patient cohort (Cohorts 1 and 2) or - 3 patients in a 20 patient cohort (Cohorts 3, 4, 5 and 6) 	Suspend recruitment and initiate review of liver safety (and any other relevant data) by safety review committee. Any further progression of the study is based on the decision by the safety review committee.

[figure not shown]
In consultation with the safety review committee, Novartis can suspend recruitment and trigger safety review any time based on safety signals including any potential Hy's law case.

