3.2 Rationale for study design

This will be a multicenter, open-label, randomized, sequential, dose escalation study in adults with uncomplicated *P. falciparum* malaria.

The objective of this dose escalation study design is to characterize hepatic safety aspects of single- and multiple ascending doses of KAE609 and determine the maximum tolerated dose of the investigational drug KAE609 in malaria patients.

Dose escalation sequential design of the study is the standard design for evaluating safety and tolerability of a new chemical entity in the early phase (Phase I and II) of clinical development. Single doses up to 75 mg and repeated dosing up to 30 mg (3 day QD) have been evaluated in patients without any significant hepatic tolerability issue with the exception of LFT elevations observed in human challenge study at 10 mg single dose and 75 mg single dose in proof of concept (PoC) extension study. Single as well as repeated doses will be evaluated in this study since knowledge about safety profile of both schedules is important to inform further development of the dosing strategy with the best benefit risk profile. Single dosing is a necessary step prior to repeat dosing and allows the detection and management of adverse events (AE) which may be more severe with repeated dosing. Hence, to characterize the safety profile of the entire dose range of KAE609, patients will be first dosed with a single dose of lowest strength i.e., 10 mg and be escalated in a stepwise manner.

Coartem will be used as reference group to help distinguish if the hepatic events and other adverse events observed in the study are exclusive to KAE609 or resulting from the disease (*P. falciparum* malaria) itself.

Coartem will be dosed in the fed state. Furthermore, KAE609 will be dosed (irrespective of fed state) as single dose or QD for 3 days whereas Coartem will be dosed as twice a day (BID) for 3 days. Considering the differences in food requirement and differential frequency of administration for both the drugs, achieving blinding for patients and investigators is not feasible. The risk of bias arising out of the open-label design is minimized due to the fact that objective endpoints have been chosen for the study.

The patient population will be described in more detail in the [Section 4](#) below

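### Section 5.5.8 sets different hepatotoxic co-medication and paracetamol rules for KAE609 and Coartem within the single 4-week ALT/AST endpoint on which they are compared

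*Protocol*

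**What the plan says.** Protocol Section 5.5.8 is split by treatment.

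- **KAE609.** Drugs "known to be potentially hepatotoxic (see [Appendix 4](#)) are prohibited for the treatment duration and 7 days after last dose". This list has no paracetamol limit.
- **Coartem.** Taking prescription drugs "is prohibited during study and within four (4) weeks prior to dosing", with emphasis on CYP3A4, CYP2D6 and QTc interactions. Neither a hepatotoxic class nor Appendix 4 is mentioned. There is an exception: "Medication which may be required to treat adverse events can be administered considering the potential interaction". On paracetamol: "Administration of paracetamol (daily total dose not to exceed 3g) / acetaminophen is acceptable", provided dose and time are documented.
- **All arms.** Section 5.5.7 allows "Paracetamol as an antipyretic, and metopimazine for repeated vomiting" and states no daily maximum for paracetamol. It requires all medication to be recorded and adds: "Each concomitant drug must be individually assessed against all exclusion criteria/prohibited medication". Herbal products are restricted to the end of the study in both lists.

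The primary variable (9.4.1) is a rise of at least two CTCAE grades in ALT or AST over four weeks. Each KAE609 group is compared with pooled Coartem by a two-sided Fisher exact test (9.4.2). SAP Table 5-8, one list for all arms, includes paracetamol in the same block as the Appendix 4 medications.

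**The concern.** The comparison is meant to separate drug from disease: "Coartem will be used as reference group to help distinguish if the hepatic events and other adverse events observed in the study" come from KAE609 or from malaria. That works best when everything else that can raise ALT or AST is handled alike in both groups. Randomization balances co-medication at entry. It cannot balance rules that diverge after assignment, and in an open-label trial the sites know which list applies.

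The KAE609 window also does not fit the liver signal. Section 3.1 says "LFT parameters, if they rise, are expected to peak within 14 days of treatment", yet the bar on hepatotoxic medications lapses earlier. A 7-day window matches the interaction items beside it, but no liver-specific reason is given. At stake are the reading of an ALT/AST difference and the escalation decisions, where three events in a 20-patient arm suspend recruitment. Patients on a suspected hepatotoxin may also be exposed to a second one during the risk period.

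**Working it through.** **1. Length of the KAE609 bar.** Study Day 1 is the first treatment day (Protocol 6.5.8). End of bar = day of last dose + 7.

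| | Single dose | 3-day regimen |
|---|---|---|
| End of bar | 1 + 7 = Day 8 | 3 + 7 = Day 10 |
| Endpoint days without bar | 29 − 8 = 21 of 29 (72%) | 29 − 10 = 19 of 29 (66%) |
| Days without bar in the Day 1–15 escalation window | 15 − 8 = 7 of 15 | 15 − 10 = 5 of 15 |

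These counts concern the medications column of Appendix 4 only. Its herbal column is covered to study end in every arm.

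**2. The rules side by side.**

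| | KAE609 | Coartem |
|---|---|---|
| Appendix 4 medications, to Day 8 or 10 | Barred, prescription or not | Prescription drugs barred except for adverse events; non-prescription ones not named |
| Appendix 4 medications, then to Day 29 | No Appendix 4 bar | As above |
| Paracetamol | Antipyretic, no stated cap | 3 g/day, dose and time documented |

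Early on, the KAE609 rule is the stricter one for non-prescription products such as NSAIDs, which Appendix 4 lists. Later it is the looser one for prescription drugs, and it is looser on paracetamol throughout. Amoxicillin-clavulanic acid shows the effect. Section 5.5.7 permits beta-lactams for a new infection and Appendix 4 lists this one. Up to Day 8 or 10 it is barred under KAE609, but a Coartem patient can receive it through the adverse-event exception. The net direction is therefore not fixed.

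**3. The plan's own figures.** Protocol 9.8.1 says that at least 3 events in 20 patients has probability below 5% at a true rate of 3% and above 90% at 30%. The binomial tail gives 2.1% and 96.5%. Protocol 9.8.2 gives 94% power for 20 versus 60 patients at 40% versus 5%; full enumeration of the Fisher test gives 94.2%. These figures are correct and unaffected.

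**4. Illustration only.** The documents give no rate of use of these drugs and no effect on ALT/AST, so the shifts below are assumptions, starting from the plan's 5% Coartem rate.

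- Shift on KAE609 alone, no drug effect, rate 5%, 8% or 10%: chance of at least 3 events in 20 is 7.5%, 21.2% or 32.3%. Chance of a significant excess over 60 Coartem patients at 5% is 1.9%, 6.4% or 11.1%.
- Shift on Coartem alone, rate 5%, 8% or 10%, KAE609 at 40%: power is 94.2%, 86.0% or 78.9%.

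The two cases pull in opposite directions. They show only that small arms are sensitive to background shifts.

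**5. Whether the analysis deals with it.** The primary analysis counts events regardless of cause. The one supportive analysis (Protocol 9.4.4, SAP 2.5.4) removes early discontinuers without an event. Neither considers co-medication.

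**The case against.** Separate lists for two drugs with different interactions are ordinary practice, and several provisions narrow the gap. A new drug in outpatient follow-up would usually treat a new complaint, which the Coartem exception allows. Known liver disease, chronic underlying disease and prohibited medication are excluded at entry in all arms. Antibiotics other than beta-lactams are to be avoided in all arms, and doubtful cases go to the medical monitor. Patients are in hospital until Day 4, when most fever treatment is likely. Protocol 7.3 requires causality assessment of liver events, with co-medication named as an alternative cause. SAP Table 2-6 gives the safety review committee concomitant medication alongside liver abnormalities, and SAP 2.4.2 tabulates prohibited drugs. There is no formal hypothesis, and results are read with narratives.

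Most of this stands as mitigation, but it does not close the gap. Checking drugs against the prohibited list leads back to the unequal windows. Table 14-2 requires no causality step for asymptomatic ALT/AST between 3 and 5 times ULN. The prohibited-drug table may be filled with permitted paracetamol if Table 5-8 is applied as printed; the final list is in a separate file that is not in the documents.

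A reader might infer that the rules bias the trial against KAE609 and inflate false triggers. The documents do not support that: no differential use is shown, and the early rule on non-prescription drugs runs the other way. Nor is Coartem left without restriction, since prescription drugs are barred throughout.

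**Conclusion.** The point holds as a minor, avoidable inconsistency. Liver-relevant co-medication rules differ by arm after randomization, and the KAE609 bar on Appendix 4 medications ends 7 days (single dose) or 5 days (3-day regimen) before the Day 15 escalation cut-off. The paracetamol cap is stated for one treatment only. These facts rest on the text and on counting Day 1 as the first dose.

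No bias is demonstrated, and neither its size nor its direction can be derived. The assumed shifts should not be quoted as an estimated effect. What remains is an alternative explanation for an ALT/AST difference, in a trial run to resolve exactly that question, which one common rule would largely remove.

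**What to change.** In the protocol, state one liver-relevant rule for all arms:

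- Avoid Appendix 4 medications through Day 29 (at minimum Day 15) unless needed to treat an adverse event.
- Limit paracetamol to 3 g/day, with dose and time recorded for every patient.
- Keep CYP-driven windows treatment-specific.

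In the SAP, do not count paracetamol permitted by Section 5.5.7 as prohibited in Table 5-8. Add a by-arm flag for primary-endpoint events preceded by an Appendix 4 drug or paracetamol.

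The cost is protocol wording, slightly tighter co-medication limits during follow-up, fuller paracetamol entries in the KAE609 arms and a small descriptive output. No visits or samples are added, because concomitant medication is already recorded.
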